## 196 **2 PROJECT OBJECTIVES AND DESIGN**

### 197 **2.1 Hypothesis and primary objective**

198 The primary objective of this study is to measure the concentration of lidocaine in the plasma of  
199 patients at the USB after an intravenous infusion with 4mg/kg lidocaine over 30 minutes.

200 We hypothesize that lidocaine concentrations in plasma of patients at the USB are inter- and  
201 intrapersonal stable and do not exceed  $5\mu\text{g/ml}$  by the end of the applied infusions.

202

#### 203 **2.1.2 Secondary objectives**

204 The secondary objectives of this study include the prospective side effects assessment of  
205 lidocaine and ketamine as well as the measurement of plasma levels of ketamine. Further, to  
206 correlate the plasma levels with the analgesic efficacy and change in possible depressive  
207 symptoms, due to the infusions.

[figure not shown]
### 208 **2.2 Primary and secondary endpoints**

209 The primary endpoint of our study is the concentration of lidocaine in the plasma of patients who  
210 received an intravenous infusion with 4mg/kg lidocaine and 0.15 – 0.5mg/kg ketamine over 30  
211 minutes at the time directly after the infusion.

212  
213 The secondary endpoints of our study are the recorded side-effects typical for lidocaine and  
214 ketamine reported by questionnaires and patient monitoring. A further endpoint of interest is the  
215 concentration of ketamine in the plasma of patients directly after the infusion. Development of  
216 pain and mood as assessed by the Short form - McGill Pain Questionnaire (SF-MPQ) and Beck  
217 Depression Questionnaire II (BDI-II), respectively.

## 218 2.3 Project design

219 This study is designed as monocentric observational pilot-study at the USB.  
220

221  
222

## 223 3 PROJECT POPULATION AND STUDY PROCEDURES

### 224 3.1 Project population, inclusion and exclusion criteria

225  
226 For our pilot project on drug plasma levels in an ambulatory infusion regime, a total of max. 15  
227 patients (10 + Drop-out of 50%) newly receiving lidocaine-ketamine infusions at the USB will be  
228 randomly selected. To minimize selection bias (including only responders, or patients with less  
229 side-effects) and because we increase the ketamine dosage normally during the first 3 infusions,  
230 we will only include patients who are new to lidocaine/ketamine infusions.

231

232 Inclusion Criteria:

233 - Patient is a new recipient of lidocaine-ketamine infusions

- 234 - Patient is 18 years of age or older
- 235 - Patient is able to provide Informed Consent
- 236
- 237 Exclusion Criteria:
- 238 - Contraindication to blood sampling (on arm not used for infusion)
- 239 - Insufficient knowledge of German language
- 240 - Inability to give consent
- 241 - Patient is under 18 years of age
- 242 - Contraindication to treatment with lidocaine and/or ketamine
- 243

### 244 **3.2 Recruitment, screening and informed consent procedure**

245 All patients who are newly assigned to lidocaine-ketamine infusions at the USB and who meet  
246 the inclusion criteria will be asked to take part in the study by their treating physician.

247 If the patients are willing to participate, they will be informed in verbal and written form by one of  
248 the investigators about the study and the blood collection.

249 All study participants will receive an informed consent form describing the study and providing  
250 sufficient information to allow participants to make an informed decision about their participation  
251 in the study. Sufficient time (at least 24 hours) will be given to the potential participants to make  
252 a decision about participation.

253 Formal informed consent will be obtained from a participant using the approved consent form  
254 before the participant undergoes any of the study procedures.

255 The consent form will be signed and dated by the investigator or his/her designee concurrently  
256 with the participant's signature. A copy of the signed consent form will be given to the study  
257 participant. The informed consent form will be retained as part of the study records.

258 The patients themselves have no direct advantage from participating in the study. The risk  
259 resulting from an additional venepuncture is to be considered minimal. The typical risks of  
260 inserting an indwelling venous cannula are already part of the infusion information. However,  
261 patients are explicitly informed that taking part in the study includes three additional venous  
262 punctures.

### 263 **3.3 Study procedures**

264 Recruitment and consent to participate in the study will take place in the consultation prior to the  
265 first infusion. (c.f. 3.2) During the infusion, the patients' vital signs will be monitored as usual (10-  
266 minute blood pressure measurement, continuous SPO2 and 5-lead ECG are recorded, c.f. 3.3.2).

267 As a part of this study, at the end of the first, second and third infusion, side effects will be  
268 screened using customized questionnaires (c.f. eCRF forms document). In addition, blood will be  
269 collected during each of the first three infusion appointments. The blood collection itself will take  
270 place within 3 minutes after termination of the infusion, as we assume the highest plasma levels  
271 at that point in time. [25, 26] For blood collection we will use a Butterfly cannula (BBraun Venofix®  
272 Safety 23G, PZN 08839883, B. Braun Melsungen AG) which will be inserted on the "non-infusion  
273 arm" and two green 7.5ml Lithium-Heparin monovettes (S-Monovette® Lithium-Heparin liquid,  
274 preparation: lithium heparin, liquid, 7.5 ml, membrane screw cap, closure green, color code ISO,  
275 (LxØ) without closure: 92 x 15 mm, with paper label, label/printing: green Sarstedt AG & Co. KG,  
276 Nümbrecht).

277 Patients will complete the Short form - McGill Pain Questionnaire (with additional recording of  
278 pain on the numeric rating scale (NRS) from 0 (no pain at all) to 10 (worst pain imaginable)) and  
279 Beck Depression Questionnaire directly prior to the first three infusions. The SF – MPQ is a  
280 validated instrument for measures of clinical pain that capture its sensory, affective and other

281 qualitative components. [27] The BDI-II provides a validated psychological test procedure that  
282 assesses the severity of depressive symptoms in adolescents 13 years of age and older and  
283 adults. [28]

284 In addition, these questionnaires will also be completed at the time points 7 days after, and 14  
285 days after the first, second and third Infusion. The participants will receive a link by e-mail so that  
286 they can fill in the questionnaires online. According to the license agreement, the BDI-II will be  
287 filled out in paper form and the results will be subsequently transferred to REDCap. If desired by  
288 the participant, these questionnaires can also be completed during a telephone survey conducted  
289 by the study staff. The surveys will be conducted with REDCap. After the third infusion, this online  
290 questioning will take place additionally after 28 days (c.f. Appendix 1). After this questioning, the  
291 study ends for the participants.

292

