#### 311 **Effects and Side effects**

312 Variable: Depressive Symptoms

313 Categories: Recorded by BDI-II at the beginning of the infusion, 7 days after and 14 days after

314 Variable: Pain

315 Categories: Recorded by SF-MPQ-2 at the beginning of the infusion, 7 days after and 14 days  
316 after, and by NRS (Number from 0 to 10) at the beginning of the infusion, 7 days after and 14  
317 days after

318 Variable: Vital signs

319 Categories: blood pressure (recorded in mmHg) / heart rate (recorded in bpm) / saturation of  
320 oxygen under infusion (recorded as percentage) / Respiratory rate (recorded in breaths per  
321 minute), recorded at the start of the infusion and subsequently during a period of 60 minutes

322 Variable: ECG

323 Categories: Heart rate (recorded in bpm), regular sinus rhythm (recorded as yes or no), PQ  
324 interval (recorded in ms), QRS-complex (recorded in ms), ST segment (recorded as  
325 conspicuous/inconspicuous), T wave (recorded as conspicuous/inconspicuous), QTc (recorded  
326 in ms), Extrasystolies (recorded as number), other anomalies (recorded as free text) at start of  
327 infusion and at the end of infusion (minute 30)

328 Variable: Side effects at end of infusion (patient recorded)  
329 Categories: Injection site pain, dysphoria, euphoria, nervousness, anxiety, dyspnea, nausea,  
330 hypersalivation, nightmares, hallucinations, visual disturbances, tinnitus, hyperacusis,  
331 paresthesias, numbness, dizziness (recorded as present/absent).

332 Variable: Side effects at end of infusion (patient observation by physician, monitoring)  
333 Categories: Exanthema, redness injection site, vomiting, tremor, dysarthria, nystagmus,  
334 convulsions, dissociation, disorientation, restlessness, agitation (recorded as present/absent)

335  
336 Variable: Medication plasma levels  
337 Categories: Lidocaine and ketamine plasma levels are recorded specified in mg/l at the end of  
338 infusions

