**Appendix 1: Schedule of assessments**

Time (days)	>-1 day	0	+7	+14	+28	+35	+42	+56	+63	+70	+84
Visit	Information	Infusion 1	Questionnaires online	Questionnaires online	Infusion 2	Questionnaires online	Questionnaires online	Infusion 3	Questionnaires online	Questionnaires online	Questionnaires online
oral and written Information	+										
Written consent	+										
check inclusion-/ exclusion criteria	+										
Medical history	+										
Participant Characteristics		+									
Questionnaires Side effects		+			+			+			
Blood Sampling		+			+			+			
Short form McGill		+	+	+	+	+	+	+	+	+	+
Beck Depression		+	+	+	+	+	+	+	+	+	+

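### The side-effect checklist has no pre-infusion value and no stated new-onset rule, so symptoms a patient already has can be recorded as side effects of the infusion

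*Protocol*

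**What the plan says.** Section 3.3 of the protocol sets the timing: "As a part of this study, at the end of the first, second and third infusion, side effects will be" screened with customized questionnaires, for which it refers to a separate eCRF forms document. The synopsis says the same.

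Section 3.3.1 defines the variable by that one time point: "Variable: Side effects at end of infusion (patient recorded"). It has 16 patient-reported items, beginning "Categories: Injection site pain, dysphoria, euphoria, nervousness, anxiety, dyspnea, nausea" and ending "paresthesias, numbness, dizziness (recorded as present/absent"). A second list of 11 physician-observed items has the same timing and scale. In Appendix 1 the row "Questionnaires Side effects" is marked only on the three infusion days (0, +28, +56).

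The other effect measures have a starting value. The ECG entry reads "in ms), Extrasystolies (recorded as number), other anomalies (recorded as free text) at start of" infusion and again at minute 30. Vital signs are "minute), recorded at the start of the infusion and subsequently during a period of 60 minutes". Pain and mood are covered by the SF-MPQ with NRS and the "Beck Depression Questionnaire directly prior to the first three infusions. The SF – MPQ is a" validated instrument for pain.

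The interview before each infusion (section 3.3.2) covers current pain, weight change, fasting and allergies. Side effects are a secondary objective (2.1.2) and a secondary endpoint (2.2). Section 4.1 has them described, and their occurrence related to dose and plasma level in exploratory linear regressions.

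**The concern.** Every patient receives both drugs at every infusion and there is no comparison group, so every checklist record is made after drug exposure. The only comparator available for a symptom is the same patient's state just before the infusion, and for this variable alone the protocol does not collect it.

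The population makes this matter. These are patients with therapy-refractory chronic pain. Section 1 itself says that chronic pain is often accompanied by depressive symptoms, can involve sensitization of the nervous system, and is commonly treated with drugs that have limiting side effects. Dysphoria, nervousness, anxiety, nausea, tinnitus, paresthesias, numbness and dizziness are all on the checklist, and all can be present before the infusion starts. A present/absent score at the end cannot tell these from symptoms the infusion caused.

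Two results are at stake: the rates reported for those items, and the exploratory relation of those items with dose and plasma level. A statistical analysis plan could not repair this, because it cannot recover a baseline that was never recorded.

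**Working it through.** **Inputs from the protocol.** 10 patients with complete data and 3 infusions each (section 4.1). The protocol's count reproduces: 10 × 3 = 30.

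**Assumed inputs.** The protocol gives no background prevalence. Let b be the share of patients who have a given symptom before the infusion (taken as 10%, 20% and 30%) and t the chance that the infusion causes it in a patient without it. A pre-existing symptom is assumed to be still present at the end of the infusion.

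**Formula.** Rate recorded at the end of infusion = b + (1 − b) × t.

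**Step 1: no drug effect (t = 0).** Expected records = 30 × b.

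- b = 10%: 30 × 0.10 = 3
- b = 20%: 30 × 0.20 = 6
- b = 30%: 30 × 0.30 = 9

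The chance that at least one of the 10 patients has the symptom beforehand is 1 − (1 − b)^10, which gives 65%, 89% and 97%.

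**Step 2: a real effect, assumed t = 20%.**

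| b | Recorded at end, 30 × [b + (1 − b)t] | New onset, 30 × (1 − b)t | Infusions free of the symptom before, 30 × (1 − b) | New onset among those |
|---|---|---|---|---|
| 10% | 8.4 | 5.4 | 27 | 20% |
| 20% | 10.8 | 4.8 | 24 | 20% |
| 30% | 13.2 | 4.2 | 21 | 20% |

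The end-only rate is 28%, 36% or 44% against a true new-onset rate of 20%. Dividing the new-onset count by the infusions free of the symptom beforehand returns the 20%.

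**Step 3: relation with plasma level.** If b is the same at high and low level, the observed difference is (1 − b) × (t_high − t_low). An assumed true contrast of 40% against 10%, which is 30 points, becomes:

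- b = 10%: 0.9 × 30 = 27 points
- b = 20%: 0.8 × 30 = 24 points
- b = 30%: 0.7 × 30 = 21 points

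**Step 4: that loss against the noise.** Splitting the 30 infusions 15 and 15 and ignoring clustering within patients, the standard error of 40% against 10% is √(0.4 × 0.6/15 + 0.1 × 0.9/15) = √(0.24/15 + 0.09/15) ≈ 0.15, or 15 points. The loss of 3 to 9 points is smaller than one standard error.

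**The case against.** The strongest objection is that the questionnaire itself is in an eCRF forms document that is not shown. The variable is named side effects, not symptoms present, and the form may ask only about what began with the infusion. This stands as a limit. A reader might infer that pre-existing symptoms are certainly counted as side effects; the protocol supports only that they can be, because it states no new-onset restriction. If the form has one, most of the problem goes, although the answer would then rest on the patient's recall directly after a ketamine infusion.

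Second, some baseline information exists: medical history before infusion 1, the brief interview before each infusion, and the SF-MPQ and BDI-II. These may document some chronic symptoms, but they are not the checklist. They give no value item by item, and no rule links them to it.

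Third, the reach is limited. A reader might infer that every side-effect rate is inflated. That does not follow: injection site pain, for example, is tied to the infusion, and the case made here is only for items that can pre-exist. Which items those are is a judgement, not a figure in the protocol.

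Fourth, the size is easily overstated. If 11 patient-reported items each pre-existed independently in 5%, 10% or 20% of patients, 1 − (1 − p)^11 would give 43%, 69% or 91% of patients with at least one. But symptoms such as anxiety and nervousness plausibly cluster, which lowers these shares, and the protocol names no any-side-effect endpoint. The single-item counts need no independence between items. They do assume that the infusion relieves no pre-existing symptom, so they are upper bounds where it does.

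Last, a stable symptom is recorded at all three infusions and creates no false dose trend within that patient. That is correct. It still raises the item's rate, and it masks any new occurrence in that patient.

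**Conclusion.** The point holds for checklist items that can exist before the infusion. As the protocol is written, such a symptom present at the end can be recorded as a side effect, and the data to separate the two are not collected. Under assumed background prevalences of 10%, 20% or 30% and no drug effect, this amounts to about 3, 6 or 9 of 30 infusions for one symptom.

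The main consequence is for the descriptive rates. The dilution of the regressions is real but modest, and small against the noise of 30 infusions. The primary endpoint, the lidocaine concentration, is untouched, as are items such as injection site pain. The conclusion rests on the absence of a new-onset restriction in the unseen form. The sizes rest on prevalences that the protocol does not give. Because the change is cheap and the missing baseline cannot be recovered later, it should be made, but it does not put the study's main aim in doubt.

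**What to change.** Give the same present/absent checklist directly before each of the three infusions, when the SF-MPQ and BDI-II are already completed. Add this time point to section 3.3, to the variable definition in section 3.3.1, to the matching synopsis text and to Appendix 1.

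In section 4.1, define a new-onset side effect as an item absent before and present after the same infusion. Report its count over the infusions in which the item was absent beforehand, alongside the raw end-of-infusion rate, and use new onset in the exploratory regressions.

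The cost is one repeated eCRF form and an estimated two extra minutes per infusion visit. One limitation remains: a present/absent scale cannot show that an existing symptom got worse, so the new-onset count misses worsening. Capturing it would need a severity grade at both times, which is a larger change to the form; without it, the limitation should be stated in the report.

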### 293 **3.3.1 Investigated variables**

294

#### 295 **Demographic**

296

297 Variable: Age

298 Categories: Age at beginning of therapy (recorded in years)

299

300 Variable: Gender

301 Categories: female / male / diverse

302

303 Variable: Nationality

304 Categories: Recorded as free text

305

306 Variable: Diagnosis that led to the indication for lidocaine/ketamine infusion

307 Categories: Main pain-related diagnosis coded with ICD11, free text

308 Variable: Dosage

309 Categories: Weight (recorded in kg) / Height (recorded in cm) / Dosage of lidocaine (recorded in  
310 mg) / Dosage of ketamine (recorded in mg)

#### 311 **Effects and Side effects**

312 Variable: Depressive Symptoms

313 Categories: Recorded by BDI-II at the beginning of the infusion, 7 days after and 14 days after

314 Variable: Pain

315 Categories: Recorded by SF-MPQ-2 at the beginning of the infusion, 7 days after and 14 days  
316 after, and by NRS (Number from 0 to 10) at the beginning of the infusion, 7 days after and 14  
317 days after

318 Variable: Vital signs

319 Categories: blood pressure (recorded in mmHg) / heart rate (recorded in bpm) / saturation of  
320 oxygen under infusion (recorded as percentage) / Respiratory rate (recorded in breaths per  
321 minute), recorded at the start of the infusion and subsequently during a period of 60 minutes

322 Variable: ECG

323 Categories: Heart rate (recorded in bpm), regular sinus rhythm (recorded as yes or no), PQ  
324 interval (recorded in ms), QRS-complex (recorded in ms), ST segment (recorded as  
325 conspicuous/inconspicuous), T wave (recorded as conspicuous/inconspicuous), QTc (recorded  
326 in ms), Extrasystolies (recorded as number), other anomalies (recorded as free text) at start of  
327 infusion and at the end of infusion (minute 30)

328 Variable: Side effects at end of infusion (patient recorded)  
329 Categories: Injection site pain, dysphoria, euphoria, nervousness, anxiety, dyspnea, nausea,  
330 hypersalivation, nightmares, hallucinations, visual disturbances, tinnitus, hyperacusis,  
331 paresthesias, numbness, dizziness (recorded as present/absent).

332 Variable: Side effects at end of infusion (patient observation by physician, monitoring)  
333 Categories: Exanthema, redness injection site, vomiting, tremor, dysarthria, nystagmus,  
334 convulsions, dissociation, disorientation, restlessness, agitation (recorded as present/absent)

335  
336 Variable: Medication plasma levels  
337 Categories: Lidocaine and ketamine plasma levels are recorded specified in mg/l at the end of  
338 infusions

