#### **Effects and Side effects**

Variable: Depressive Symptoms

Categories: Recorded by BDI-II at the beginning of the infusion, 7 days after and 14 days after

Variable: Pain

Categories: Recorded by SF-MPQ-2 at the beginning of the infusion, 7 days after and 14 days after, and by NRS (Number from 0 to 10) at the beginning of the infusion, 7 days after and 14 days after

Variable: Vital signs

Categories: blood pressure (recorded in mmHg) / heart rate (recorded in bpm) / saturation of oxygen under infusion (recorded as percentage) / Respiratory rate (recorded in breaths per minute), recorded at the start of the infusion and subsequently during a period of 60 minutes

Variable: ECG

Categories: Heart rate (recorded in bpm), regular sinus rhythm (recorded as yes or no), PQ interval (recorded in ms), QRS-complex (recorded in ms), ST segment (recorded as conspicuous/inconspicuous), T wave (recorded as conspicuous/inconspicuous), QTc (recorded in ms), Extrasystolies (recorded as number), other anomalies (recorded as free text) at start of infusion and at the end of infusion (minute 30)

Variable: Side effects at end of infusion (patient recorded)

	
Categories: Injection site pain, dysphoria, euphoria, nervousness, anxiety, dyspnea, nausea, hypersalivation, nightmares, hallucinations, visual disturbances, tinnitus, hyperacusis, paresthesias, numbness, dizziness (recorded as present/absent).
 
Variable: Side effects at end of infusion (patient observation by physician, monitoring)
 
Categories: Exanthema, redness injection site, vomiting, tremor, dysarthria, nystagmus, convulsions, dissociation, disorientation, restlessness, agitation (recorded as present/absent)
 
Variable: Medication plasma levels
 
Categories: Lidocaine and ketamine plasma levels are recorded specified in mg/l at the end of infusions
 
Laboratory Analysis
 
Samples were analyzed on a Thermo Scientific™ Orbitrap Exploris™ 240 Mass Spectrometer coupled to reversed phase liquid chromatography with an LLOQ of 0.1 µmol/L for lidocaine and 0.1 mg/L for ketamine. The methods were fully validated according to EMA guideline.

Number of Participants with Rationale:	A total of max. 15 patients (10 + Drop-out of 50%) will be included.
Study Duration:	In total, we expect a study duration of 7 months. Study duration for each individual participant will be 12 weeks.
Study Schedule:	First-Participant-In: 06/2023 Last-Participant-Out: 12/2023

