### 339 3.3.2 Standard Procedure of lidocaine-ketamine infusions at the Pain Unit of USB

340  
341 During a short medical history interview Patients are briefly asked about their current pain  
342 situation before each infusion. For safety reasons, additional questions are asked about weight  
343 changes, compliance with fasting (= no solid food for 6 hours, no drinks for 2 hours) and allergies.

344 Monitoring is then installed (10-minute blood pressure measurement, continuous SPO2 and 5-  
345 lead ECG are recorded) and venous access is established. Lidocaine and ketamine are infused  
346 over a period of 30 minutes. The dosage of lidocaine is 4mg/kg is maintained throughout the  
347 infusions, and the dosage of ketamine is increased within the first three infusions from 0.15mg/kg  
348 at the first, to 0.25mg/kg at the second and 0.5mg/kg at the third infusion. In case patients already  
349 experiencing sufficient analgesic effect and/or improvement in quality of life after the 1st or 2nd  
350 infusion or if side effects do not allow a further dose increase, no further step up of ketamine  
351 dosage is made. We define a sufficient effect as a significant pain reduction (more than 50%) for  
352 at least 2 weeks and/or better quality of life with improved functionality during at least 2 weeks.

353 After the infusion, patients are monitored for at least another half hour, are discharged in company  
354 and are instructed to not run heavy machines and motor vehicles for at least 24 hours.

355

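### The printed side-effect lists have no free-text item, and the protocol states no route by which a reaction outside them reaches the side-effect endpoint

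*Protocol*

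**What the plan says.** Section 2.2 defines the endpoint: "The secondary endpoints of our study are the recorded side-effects typical for lidocaine and" ketamine, as reported by questionnaires and patient monitoring.

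Section 3.3.1, under Effects and Side effects, gives the variables, and the synopsis repeats them. The patient-recorded list opens "Injection site pain, dysphoria, euphoria, nervousness, anxiety, dyspnea, nausea" and continues "hypersalivation, nightmares, hallucinations, visual disturbances, tinnitus, hyperacusis, paresthesias, numbness, dizziness (recorded as present/absent". The physician-observed list closes "convulsions, dissociation, disorientation, restlessness, agitation (recorded as present/absent".

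In the same section the ECG variable includes "other anomalies (recorded as free text) at start of" and at the end of the infusion. Vital signs are "minute), recorded at the start of the infusion and subsequently during a period of 60 minutes".

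Section 3.3 says that the side-effect questionnaires are customised and refers to a separate eCRF forms document. Section 4.1 plans a mainly descriptive analysis of side effects (item 3) and exploratory regressions relating dose and plasma levels to pain, mood and the occurrence of side effects (item 4).

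**The concern.** Prospective assessment of side effects is a stated secondary objective (section 2.1.2). Section 6.2 hopes to adapt the infusion regimens from plasma levels correlated with effects and side effects. That requires a reaction to have somewhere to be recorded, and a stated path from the record to the analysis. For a reaction that is not among the printed items, the protocol shows neither.

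A statistical analysis plan could still define the summary, but it cannot supply a field that was not on the form. An observation not written down at the end of an infusion is hard to recover later.

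Side effects also influence exposure. Under section 3.3.2 the ketamine dose is not stepped up if side effects do not allow it. An unlisted reaction could therefore hold the dose at the second or third infusion. The item 4 regressions would then contain the changed dose but not the reaction that caused it.

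**Working it through.** No power or significance figure bears on this point, and the protocol states no item total. The check is a count, followed by a search for other routes into the endpoint.

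**Count of items (section 3.3.1, same in the synopsis)**
- Patient-recorded: 7 from injection site pain to nausea, plus 9 from hypersalivation to dizziness = 16.
- Physician-observed: 6 from exanthema to nystagmus, plus 5 from convulsions to agitation = 11.
- Total: 16 + 11 = 27, all different.
- Items for sedation, drowsiness, somnolence, fatigue, tiredness or sleep: 0.
- Items for *other* or free text: 0.

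**Routes by which an unlisted reaction might reach the endpoint**
1. *Questionnaires.* The printed lists have no field for it. The eCRF forms document might, but it is not at hand.
2. *Monitoring.* Blood pressure, heart rate, oxygen saturation, respiratory rate and ECG are recorded. These would pick up a cardiorespiratory effect, and the ECG has free text. They do not record a symptom or the level of alertness.
3. *Adverse events.* Section 7.2 names AEs and SAEs as source data, and section 3.4 makes certain AEs a reason for withdrawal. Appendix 1 has a row for the side-effect questionnaires but none for AEs. Neither section 2.2 nor section 4.1 says that AEs count towards the side-effect endpoint.
4. *Serious events.* The footnote to section 5.3 covers only serious events for which attribution to sampling or data collection cannot be excluded. A reaction attributable only to the infused drugs falls outside it.

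None of the four is a stated route from an unlisted symptom to the table in item 3 or the regressions in item 4.

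**Size of the extra work**
- Planned complete data: 10 patients x 3 infusions = 30 infusions.
- Upper limit with replacements: 15 patients x 3 infusions = 45 infusions.

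**The case against.** The strongest reply is that the protocol nowhere says the list is exhaustive. The instrument itself is in the eCRF forms document, which may already hold an *other* field. AEs are recorded, and section 4.1 speaks of side effects during treatment in general, without limiting the analysis to the 27 items. All of this stands, so the point has to be conditional: the route is unstated, not ruled out. If the form does have the field, the protocol and the form differ and section 3.3.1 should be brought into line.

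It can also be said that no passage mentions sedation or calls it typical of these drugs. That stands too, and for this reason the free-text line is the main request and the drowsiness item only a preference. The free-text line needs no premise about which reactions occur.

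A reader might infer more from the discharge rule, under which patients leave accompanied "and are instructed to not run heavy machines and motor vehicles for at least 24 hours", namely that the checklist cannot register the impairment this rule guards against. The documents do not support that. The rule names no symptom, and dizziness, visual disturbances, hallucinations, dissociation and disorientation are all listed and bear on driving.

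A reader might also infer that a missing effect would be published as a zero rate. It would be absent from the table, which is different.

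**Conclusion.** The point holds in a limited form and is minor. As printed, 0 of 27 side-effect items are open and 0 concern drowsiness or sedation, and no passage says how a reaction outside the list, or an AE under section 7.2, enters the side-effect endpoint. Such a reaction would be missing from the descriptive summary and the regressions.

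This assumes that the eCRF form follows the printed lists, which cannot be checked here. No number of missed events is offered. The documents give no rate for any unlisted reaction, and multiplying an assumed rate by 30 infusions would only restate the assumption. The infusions also come three to a patient and cannot be treated as independent.

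The lidocaine plasma level, the primary endpoint, is unaffected.

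**What to change.** - In section 3.3.1, the synopsis and the eCRF, add *other (free text)* to both the patient-recorded and the physician-observed list, preferably with a drowsiness/sedation item in each. If the eCRF already has such fields, amend the protocol text to match.
- In section 4.1, item 3, state that these entries and any AEs recorded at the infusion visits are included in the side-effect summary.

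The cost is at most two more entries on each of two short checklists at visits that already take place, and coding of free text for at most 45 infusions. No visit, dose or clinical rule changes.
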